Hypothesis 4A: Patients receiving BCA grafts will have lower complication rates at 1 and 2 years follow up than those who receive ePTFE grafts.

Specific Aim 5: To compare re-intervention rates between BCA and ePTFE

Hypothesis 5A: Patients receiving BCA grafts will have a lower re-intervention rate at 1 and 2 years follow up than those who receive ePTFE grafts.

Primary outcomes: Primary, primary assisted and secondary patency rates at 1 and 2 years.

Secondary outcomes: Complication (pseudoaneurysms, infections and steal syndrome) and re-intervention rates at 1 and 2 years.

3. Background

It is known that arteriovenous fistulae (AVF) confer a clear benefit for hemodialysis access in patients with end stage renal disease (ESRD). As a result, national guidelines stipulate AVF as the preferred mode of permanent hemodialysis access¹. In practice, not all patients are good candidates for AVF due to unavailable or inadequate venous conduit(s). In these patients, arteriovenous grafts (AVG) serve as reliable substitutes.

Synthetic grafts such as those made from expanded polytetrafluoroethylene (ePTFE) are the most common AVG's in current use. However, significant drawbacks of ePTFE have been reported in relation to long term patency and infection rates²⁻⁴. These inadequacies inform the need to develop and evaluate biologic conduits that achieve closer mimicry of native human vessels and as result may overcome the disadvantages associated with synthetic grafts.

Since the use of bovine carotid artery (BCA) biological grafts began in the 1970's⁵⁻⁸, significant advances have been made in conduit design and techniques for AVG placement and postoperative endovascular

management. Despite the wide spread use of ePTFE, there is lack of current evidence of a clear advantage of ePTFE over biologic conduits. Prior comparative studies were based on patient cohorts drawn from prior decades^{9,10,11}. This questions the bases for the preference of synthetic conduits in this age. In addition to this lack of current evidence, the more recent study was based on a small cohort of patients¹⁰. Consequently, these inadequately powered studies were unable to establish superiority between AVG options.

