All data will be stored in a secure database housed by the Vascular and Endovascular Clinical Research Center at Johns Hopkins Bayview Medical Center. Data cleaning and resolution of queries will be carried out continuously through the study period. Univariate methods (Chi Square, ANOVA, t-test) will be employed to compare patients' characteristics. Kaplan Meier and Multivariate Cox proportional regression analyses will be employed to evaluate and compare outcomes between BCA and ePTFE over time. Interim statistically analysis every 6 months between the cohorts will be performed to ensure unbiased distribution of possible confounders. If a bias is found (uneven comorbid conditions distribution), an effort will be made to correct it. All analyses will be performed using Stata version 12.1 (Statacorp, College Station, Texas). P-values less than 0.05 will be accepted as significant.

Sample Size

Specific Aims 1-3

Based on data from a prior study¹⁰ primary assisted patency of BCA was 60.5% and 40.5% at 1 and 2 years respectively. Primary assisted patency of ePTFE was 20.8 and 13.8% at 1 and 2 years, respectively. Based on an 80% power and an alpha of 0.05, the minimum sample size required to detect a 30% difference in assisted patency in a two-tailed comparison of BCA vs. ePTFE is 49 patients per group (for a total of 98 patients).

Specific Aim 4

Based on data from a prior study¹⁰, complication rates were 0.77 in ePTFE and 0.34 in BCA. Based on an 80% power and an alpha of 0.05, the minimum sample size required to detect a 30% difference in complications in a two-tailed comparison of BCA vs. ePTFE is 47 patients per group (for a total of 94 patients).

Specific Aim 5

Based on data from a prior study¹⁰, the total number of intervention for BCA was 1.45 ± 0.19 and 1.99 ± 0.25 for ePTFE⁶. Based on an 80% power and an alpha of 0.05, the minimum sample size required to detect a 20% difference in intervention rates in a two-tailed comparison of BCA vs. ePTFE is 47 patients per

Based on these estimates, this study will be conducted on a minimum sample of 100 patients with 50 patients in each treatment arm.

- d. Early stopping rules.
 - 1. Inability to tolerate BCA graft
 - 2. Allergic reaction to the BCA graft
 - 3. Statistical evidence that the BCA has better outcomes versus the standard ePTFE*

*we will carry out a review of the outcomes every 6 months in this study

8. Risks

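### Specific Aim 5's 47 per group for a 20% difference in interventions cannot be reproduced from 1.45 ± 0.19 versus 1.99 ± 0.25 without an input the protocol does not state

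*Combined protocol and SAP*

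**What the plan says.** Section 7c (Sample Size, Specific Aim 5) takes its inputs from a cited prior study: "the total number of intervention for BCA was 1.45 ± 0.19 and 1.99 ± 0.25 for ePTFE". With 80% power and alpha 0.05 it then gives the number needed to "detect a 20% difference in intervention rates in a two-tailed comparison of BCA vs. ePTFE is 47 patients per" group. The supplied text breaks off there. Effect, power, alpha, sidedness and n all come before the break, so nothing here turns on the missing words.

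The protocol does not say whether ± is a standard deviation (SD) or a standard error (SE), what period the counts cover, which arm the 20% refers to, or which test was used.

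The neighbouring calculations are "49 patients per group (for a total of 98 patients" for Aims 1-3 and "47 patients per group (for a total of 94 patients" for Aim 4, the latter resting on "complication rates were 0.77 in ePTFE and 0.34 in BCA". Taking the aims together, the protocol concludes that "this study will be conducted on a minimum sample of 100 patients with 50 patients in each treatment arm".

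The hypothesis for Aim 5 (section 2) is that "Patients receiving BCA grafts will have a lower re-intervention rate at 1 and 2 years follow up". The outcome analysis in section 7c is described in one sentence: "Kaplan Meier and Multivariate Cox proportional regression analyses will be employed to evaluate and compare outcomes between BCA and ePTFE over time".

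**The concern.** Re-intervention has its own aim and hypothesis and is a listed secondary outcome. Its power statement is the only guide to what a null result on it would mean. The quoted means differ by 0.54, which is 27% of 1.99 or 37% of 1.45, yet the effect sized is 20%. The quoted ± values are small relative to any 20% effect, so a comparison of means using them as SDs would need far fewer than 47 per group. If they are SEs, or if the counts vary roughly as Poisson counts, the requirement could be far larger. A reader cannot tell what re-intervention effect 50 per arm can detect at 1 or 2 years.

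**Working it through.** **Inputs (section 7c).** Two-sided alpha 0.05, power 80%, 1:1 allocation (section 4a), means 1.45 and 1.99, ± 0.19 and 0.25. Three readings of the 20% effect d: 0.20 × 1.99 = 0.398; 0.20 × 1.45 = 0.29; absolute 0.20.

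**Formula.** n per group = (1.960 + 0.842)² (v1 + v2) / d² = 7.849 (v1 + v2) / d², rounded up.

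**1. Trying to reproduce 47 with ± as SD.** v1 + v2 = 0.19² + 0.25² = 0.0986.

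| d | n per group | Power at 50 per arm | Common SD that would give 47: d√(47/2)/2.802 |
|---|---|---|---|
| 0.398 | 4.9 → 5 | >99.9% | 0.69 |
| 0.29 | 9.2 → 10 | >99.9% | 0.50 |
| 0.20 | 19.3 → 20 | 99.5% | 0.35 |

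An exact t-test calculation gives 7, 11 and 21. None is near 47.

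**2. ± as SE.** SD² = m × SE², where m is the prior study's patients per arm. Setting n = 47 gives m = 47 d² / (7.849 × 0.0986) = 9.6, 5.1 and 2.4 for the three readings. The documents give no arm size. If m were between 20 and 100 (an assumption), d = 0.398 would need 98 to 489 per group, and power at 50 per arm would be about 52% down to 14%.

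**3. Poisson counts (an assumed model; variance = mean, the ± values unused).** The second figure in each row treats the means as annual rates over two full years, which halves n.

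| Comparison | n per group, total counts | n per group, 2 full years | Power at 50 per arm |
|---|---|---|---|
| 1.99 vs 1.592 (20%) | 7.849 × 3.582 / 0.398² = 177.5 → 178 | 88.7 → 89 | 32% / 56% |
| 1.45 vs 1.16 (20%) | 7.849 × 2.61 / 0.29² = 243.6 → 244 | 121.8 → 122 | 24% / 43% |
| 1.99 vs 1.45 (27%) | 7.849 × 3.44 / 0.54² = 92.6 → 93 | 46.3 → 47 | 54% / 83% |

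The last row does return 47, but only for the full 27% difference, with the quoted total numbers taken as yearly rates and every patient followed for two years. It is not the stated 20%.

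**4. Another near match.** Taking 20% of the 0.54 gap (d = 0.108) with SD 0.19 alone gives 49. With both SDs it gives 7.849 × 0.0986 / 0.108² = 66.4 → 67. This is a strained reading and still not 47.

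**5. The other aims, as a check.** Two proportions, 30-point difference, with continuity correction: n = (n₀/4)[1 + √(1 + 4/(n₀d))]², where n₀ is the uncorrected n.

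- Aims 1-3, 0.605 vs 0.305: n₀ = 42.05, corrected 48.5 → 49, as stated.
- Aim 4, 0.77 vs 0.47: n₀ = 39.89, corrected 46.3 → 47, as stated.

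**6. What 50 per arm could detect.** Under assumed Poisson with no losses, solving 7.849 × 1.99(2 − r) / (1.99r)² = 50 gives r = 36% below 1.99 on total counts. With doubled exposure r = 26%. Overdispersion or losses would make both larger.

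**The case against.** The strongest reply is that the figure is uncheckable rather than disproved. If ± is an SE and the prior study was very small, 47 and 80% power do follow. The documents neither give nor exclude such an arm size, so one cannot say that no reading yields 80%. This stands, and the point is limited accordingly: 47 needs an input that the protocol does not state.

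A reader might infer that Aim 5 is underpowered. The documents do not support that. The low powers come from an assumed Poisson model or from assumed prior arm sizes; the plain SD reading gives power above 99%.

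A reader might also infer that 47 was carried over from Aim 4. The two numbers are equal, but nothing shows where Aim 5's came from.

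The contrast with the other aims is supportive, not decisive. The matches use BCA as reference for Aims 1-3 and ePTFE for Aim 4; swapping reference arms gives 46 (0.208 vs 0.508) and 49 (0.34 vs 0.64).

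Finally, the plan does not say that its Cox model is limited to first events, and Cox models can be extended to recurrent events. The mismatch between sizing on a count and analysing by Kaplan-Meier and Cox is therefore a secondary matter of clarity, not a demonstrated error.

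**Conclusion.** The point holds in this form: the claim of 80% power for a 20% difference with 47 per group is not supported by the inputs given for it. Under the SD reading, the stated n is roughly 2 to 9 times what the formula requires (47/20 = 2.4; 47/5 = 9.4). Under assumed Poisson, a 20% reduction from 1.99 needs roughly 2 to 4 times the stated n (89/47 = 1.9; 178/47 = 3.8). Under the SE reading, the answer depends on a prior arm size that is not given. The direction of the error therefore depends on what ± means.

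The consequence is bounded. Re-intervention is a secondary outcome, and the 49 per group of Aims 1-3 supports 50 per arm by itself. What is lost is the ability to interpret the Aim 5 result, above all a null one. The statement should be corrected, but it does not threaten the design.

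**What to change.** Withdraw the Aim 5 power statement or recompute it. If it is recomputed, state whether ± is an SD or an SE (with the prior arm size if an SE), the time unit of the counts, the reference arm and scale of the 20%, and the test or count model. Then state what 50 per arm can detect with 80% power under that model, allowing for losses and overdispersion. The 36% and 26% reductions above illustrate the form of such a statement; they are not values to adopt without checking the model.

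As a secondary change, because Aim 5 is sized on a mean count above 1 per graft, say that it will be analysed as a count or rate using each patient's follow-up time, by a rate or recurrent-event model, with a rate ratio and 95% confidence interval, rather than by first-event Kaplan-Meier and Cox alone.

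The cost is protocol wording, possibly a less favourable stated power, and a little more analysis work. The sample size does not change.

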3) Thereafter; dialysis center 3 times weekly: The graft will be monitored for its functionality during dialysis sessions three times weekly by the nephrologists or trained dialysis nurses. Difficulty during dialysis (disruptions in flow pattern or increased bleeding) or the absence of a thrill or bruit will warrant surgical evaluation. If by physical examination the graft is thrombosed, then the patient will immediately be referred for endovascular thrombectomy and revision. If the graft is patent, but problematic, the patient will be referred for an urgent fistulogram and endovascular intervention.

Patients, dialysis and dialysis access centers will be contacted by the fellow or study coordinator **every three months up to two years** to ascertain function of the graft and monitor outcomes of interest.

Note: This time frame for follow up was chosen because:

- a) It will minimize data lost to follow up.
- b) It will maximize the opportunity for detection of infection, malformations or stenoses since most graft abnormalities are apparent by 30 days postoperatively.
- c) The standard of care at the Johns Hopkins surgical department includes a post-op check and visit 5 to 14 days following surgery.
- d) The follow up continues up to 2 years to report the final outcomes at end of the study.

Outcomes

Outcomes will be assessed and documented per standards for reports dealing with arteriovenous hemodialysis access¹³ and defined as follows. Primary patency: Interval from graft placement to any intervention for stenosis with or without complete occlusion (thrombosis). Assisted primary patency: interval from graft placement to the first episode of complete occlusion. Secondary patency: interval from graft placement to graft failure. Functional patency: interval from first time graft is used for hemodialysis to qualifying event as above. Infection will be defined as the presence of erythema or purulent drainage at

the surgical incision and need for intravenous antibiotics or surgical intervention. Steal syndrome will be staged per standard as follows: Stage I: pale/blue and/or cold hand without pain; Stage II: Pain during exercise and/or hemodialysis; Stage III: Rest pain; Stage IV: Ulcers/necrosis/gangrene. Accordingly, surgical intervention will be carried out for patients with stage III or IV steal.

Innovation

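### The rule to stop when BCA is statistically better (section 7d, item 3) names no outcome, test, total number of reviews or boundary; at P<0.05 per review, the false-win rate for BCA would be about 5-9% against 2.5%

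*Combined protocol and SAP*

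**What the plan says.** Section 7d (Early stopping rules), item 3, permits stopping on "Statistical evidence that the BCA has better outcomes versus the standard ePTFE". Its footnote adds: "we will carry out a review of the outcomes every 6 months in this study".

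Section 7c (Statistical plan) supplies what else there is:

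- Methods: "Kaplan Meier and Multivariate Cox proportional regression analyses will be employed to evaluate and compare outcomes between BCA and ePTFE over time".
- Threshold: "P-values less than 0.05 will be accepted as significant". No other significance level for a comparison appears in the document.
- Interim work: "Interim statistically analysis every 6 months between the cohorts will be performed to ensure unbiased distribution of possible confounders". No efficacy boundary is attached to it.
- Sizing for Aims 1-3 gives 49 per group, for a two-sided test, on this basis: "Based on an 80% power and an alpha of 0.05, the minimum sample size required to detect a 30% difference in assisted patency". The trial then plans 50 per arm.

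Section 2 (Objectives) gives "Primary outcomes: Primary, primary assisted and secondary patency rates at 1 and 2 years". Section 4b follows patients for up to 2 years and starts the functional-patency clock at first use of the graft for dialysis.

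**The concern.** A stopping rule for benefit is a decision rule, and its false-positive rate depends on what is tested, how often and against what limit. Item 3 fixes only the interval between tests. At a 6-month review, someone asked whether there is statistical evidence has one criterion in the plan to turn to, P<0.05. The sample size, however, spends the whole 0.05 on one test. Each unadjusted look adds another chance of a false declaration that BCA is better.

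Two things are at stake. First, the error rate of a BCA win would depend on choices left open until outcome data have been seen, in a trial that section 4c leaves unblinded. Second, no patient can have 2 years of follow-up at the 6-, 12- or 18-month review. If stopping ended follow-up as well as accrual, the 2-year half of the primary outcomes would not exist, and no later analysis could restore it.

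**Working it through.** **1. The plan's own figure.** Take 60.5% for BCA (1-year assisted patency, section 7c) against 60.5 − 30 = 30.5%, two-sided 0.05, 80% power. The mean proportion is 0.455.

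- n = [1.960√(2 × 0.455 × 0.545) + 0.842√(0.605 × 0.395 + 0.305 × 0.695)]² / 0.30² = (1.380 + 0.565)² / 0.09 = 42.05, or 43.
- With continuity correction: (42.05/4) × [1 + √(1 + 4/(42.05 × 0.30))]² = 48.5, or 49.

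The stated 49 is reproduced. The design therefore assumes a single two-sided 0.05 test, or 2.5% in BCA's favour.

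**2. Number of reviews.** Accrual time is not given. Assuming 0, 12, 24 or 36 months, and a last look 24 months after accrual ends, reviews = (accrual + 24)/6 = 4, 6, 8 or 10.

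**3. Null curve.** Both arms follow the mean of the two prior-study arms in section 7c: (60.5 + 20.8)/2 = 40.65% at 1 year and (40.5 + 13.8)/2 = 27.15% at 2 years. There are 50 patients per arm, uniform accrual and at most 24 months' follow-up. A false win is z > 1.96 in BCA's favour at any review. Sensitivity runs also used the ePTFE curve, the BCA curve and a 75%/60% curve.

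**4. False-win rate for BCA, one outcome, P<0.05 at each review.**

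| Test and handling of early reviews | 4 reviews | 6 | 8 | 10 |
|---|---|---|---|---|
| Equal information steps (reference) | 6.3% | 7.7% | 8.9% | 9.7% |
| Log-rank, no test below 5 events, mean curve, first use at 1 month (40,000 runs) | 5.4% | 7.1% | 8.0% | 9.0% |
| Log-rank, every review, four curves | 4.6-6.2% | 6.5-7.5% | 8.1-9.2% | 9.1-10.6% |
| Log-rank, no test below 10 events, four curves | 4.8-6.0% | 5.7-6.4% | 6.4-7.4% | 6.7-8.8% |
| Cox Wald, every review, four curves | 4.6-5.1% | 5.2-5.9% | 5.9-6.9% | 6.0-8.4% |

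A single final log-rank test gives 2.4-2.7%, so the excess comes from the repeated looks. Changing the assumed delay to first use to 0 or 2 months gives 5.1/7.2/8.2/9.1% and 5.7/6.8/7.9/9.1% in the 5-event row. The Cox model had treatment only, because the plan does not list the covariates of its multivariate model.

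**5. An example boundary.** Use two-sided P<0.001 at interim reviews and 0.05 at the end (Haybittle-Peto). Each interim adds at most 0.1 point, so the ceiling is 5 + 3 × 0.1 = 5.3% with 4 reviews and 5 + 9 × 0.1 = 5.9% with 10. Integration over the simulated information fractions gives 5.03, 5.12, 5.19 and 5.25% for 4, 6, 8 and 10 reviews, with power of 80.0-80.1%. An O'Brien-Fleming-type boundary on the same fractions has a final P of about 0.036-0.040 and power of 78.7-78.9%.

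**6. How often P<0.001 stops the trial early.** For 4/6/8/10 reviews, the prior-study patency (60.5%/40.5% against 20.8%/13.8%) gives 86/85/84/83%. The 30-point difference (60.5%/40.5% against 30.5%/20%, the 2-year control value being assumed) gives 46/46/45/44%.

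**The case against.** The strongest reply is that the size is conditional at every step. The plan never says that P<0.05 is the interim boundary; that is its general threshold. The number of reviews is assumed. The planned Cox analysis is more conservative than log-rank when events are few: at 10 reviews, 6.0-8.4% against 9.1-10.6%. Skipping sparse reviews lowers the log-rank rates. Item 3 speaks of outcomes in the plural, and other readings give other rates. If all three patency outcomes must cross at one review, the rate is 0.6-0.9% in the base case, below nominal. If assisted patency is tested as a 1-year proportion, it is 4.4/6.6/8.0% for 6/8/10 reviews, with no inflation if all grafts are placed at once. All of this stands, and it limits the claim to a conditional range. It does not remove the gap, because nothing in the document selects among these readings.

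A reader might infer that 7c and 7d contradict each other, since 7c describes its 6-monthly analysis as a check on confounder balance. They do not: a balance check and an outcome review can both take place. What is missing is a statement of whether the review includes an efficacy test.

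It can also fairly be said that item 3 is not silent on timing. The footnote fixes the interval; only the total number of reviews is open.

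**Conclusion.** The point holds as an unspecified efficacy-stopping rule and should be settled before any outcome review. If P<0.05 is applied at each review to one time-to-event patency outcome, the false-win rate for BCA is about 5-8% by Cox Wald and about 5-9% by log-rank (5-event minimum). That is two to a little over three times the nominal 2.5% by Cox (8/2.5 = 3.2) and up to 3.6 times by log-rank (9/2.5). The range rests on 4 to 10 reviews, accrual of 0-36 months, the assumed patency curves and no covariates. Complications and re-interventions were not simulated.

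Two stronger readings are not supported. The documents do not show that the trial's error rate is inflated by a known amount, because they do not state the interim criterion. Nor do they say that stopping would end follow-up; the loss of 2-year data follows only if it does. Multiplicity across the three primary patency outcomes is a separate matter and forms no part of this conclusion.

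**What to change.** Amend the protocol before any outcome review, in one of two ways.

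- **No efficacy stopping intended:** delete item 3 of section 7d and its footnote, and say in 7c that the 6-monthly reviews carry no efficacy stopping.
- **Efficacy stopping intended:** name one patency outcome, its test, the review schedule and an error-controlling boundary, and state whether stopping ends accrual only or follow-up too. The outcome is the sponsor's choice; assisted primary patency is the one used for sizing.

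Two-sided P<0.001 at interim reviews with 0.05 at the final test is one suitable boundary. An O'Brien-Fleming-type spending boundary, computed from the actual information at each review, is another.

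The cost is an amendment with IRB approval and no extra patients. With the first boundary the loss of power is negligible; with the second, 80% becomes about 79%. The real downside is less frequent early stopping. At P<0.001 the trial would stop early in about 44-46% of runs under the 30-point difference it is sized for, and in 83-86% only under the larger prior-study difference.

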This study addresses the need for an objective comparison of contemporary AVG options available to patients and their surgeons. The key innovative aspects of this study are:

1. Randomization of patients to minimize the effects of measured and unmeasured confounders.
2. Study of a present-day cohort of patients so as to derive evidence applicable to contemporary practice.
3. Study of a sample of patients large enough to achieve statistical and clinically significant results.

In this study we will conduct a randomized comparison of bovine carotid artery biological grafts (Artegraft®; Artegraft, Inc., North Brunswick, NJ) to standard polytetrafluoroethylene grafts. Our goal is to establish differences in patency (functional, primary, primary assisted and secondary), complication and intervention rates.

Problems and solutions

Despite our conservative estimate, we are prepared for the possibility of inadequate enrollment in this study. In the event that we are unable to achieve a sample of patients required for well-powered analyses, we will extend patient recruitment to other hospitals on the Johns Hopkins Medical Institution network. This large back up pool of patients is reassuring.

- c. Blinding, including justification for blinding or not blinding the trial, if applicable.

This study will not be blinded because patient side blinding is expected to have minimal to no effect, while physician side blinding is impractical and difficult to achieve due to the primary surgeon being the one usually who follows up on any future interventions or treatments.

- d. Justification of why participants will not receive routine care or will have current therapy stopped.

All participants will receive routine care and will not have current therapy stopped.

- e. Justification for inclusion of a placebo or non-treatment group. **Not applicable**

- f. Definition of treatment failure or participant removal criteria.

In case of intolerance or development of an allergic reaction (such as severe incision site skin irritation or discomfort) the PI or co-PI will decide whether to remove the graft or replace it and the patient's hypersensitive reaction will be treated according to best medical practice.

5. Inclusion/Exclusion Criteria

Inclusion criteria

1. Patient must be at least 18 years of age.

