- a. Medical risks, listing all procedures, their major and minor risks and expected frequency.

Generally speaking there is minimal risk in participating in this study. If the patient is randomized to the standard ePTFE, they will receive our hospital's standard of care for ePTFE AVG. If the patient is randomized to the BCA graft they may experience the following:

- 1. Discomfort and inability to tolerate the BCA graft: In this situation the graft will be inspected by the Principle Investigator, co-PI or wound nursing team. In the event that the patient is still unable to tolerate the graft, it will be removed or replaced and the patient will be excluded from the study.
- 2. Skin abrasion or irritation: If on inspection the skin edges at the incision site appear to be red or irritated the PI, co-PI or wound nursing team will inspect the site of operation and determine whether the graft needs revision or removal.
- 3. Allergic reaction to the device: Since BCA is an acellular collagen matrix, it is tested as non-antigenic and packaged sterile in its container. However, any foreign material may cause a reaction. If at any time during the study the patient appears to have an allergic

reaction to the BCA. The Principle Investigator or co-PI will determine if the graft needs to be removed and the patient will be removed from the study.

4. Redness or erythema, fever, signs of infection: Should there be any concern for infection of the graft, the surgery site will be assessed by the Principle Investigator, co-PI, Nurse Practitioner or Physician Assistant. Appropriate standard of care will be initiated should the wound indeed be infected. This may include opening and draining the incision, wet to dry dressing changes and antibiotics treatment.

b. Steps taken to minimize the risks.

Follow standard surgical procedures and placement of AVG.

c. Plan for reporting unanticipated problems or study deviations.

All events will be reported to the JHM IRB as required by the JHM IRB reporting guidelines posted on the JHM IRB website.

d. Legal risks such as the risks that would be associated with breach of confidentiality.

There should be no legal risks by participating in this study. None beyond those associated with routine care.

e. Financial risks to the participants.

None beyond those associated with routine care.

9. Benefits

a. Description of the probable benefits for the participant and for society.

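### Section 8a takes BCA patients off study for intolerance or allergy, with no written ePTFE counterpart and no analysis rule, so secondary patency can be biased toward BCA

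*Combined protocol and SAP*

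**What the plan says.** Section 8a introduces its list with "If the patient is randomized to the BCA graft they may experience the following", so what follows covers the BCA arm only. Item 1 ends, for persistent intolerance: "unable to tolerate the graft, it will be removed or replaced and the patient will be excluded from the study". Item 3 says that after an allergic reaction the investigators are to "determine if the graft needs to be removed and the patient will be removed from the study". It is unclear whether item 3 takes the patient off study only when the graft comes out, or after any allergic reaction. For ePTFE, section 8a promises standard care and gives no off-study rule.

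Section 4f is headed "Definition of treatment failure or participant removal criteria" and names no arm. Its text leaves the investigator to decide on removing or replacing the graft. It does not say that the patient leaves the study, or how the event is analysed.

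Section 7d lists "Inability to tolerate BCA graft" and "Allergic reaction to the BCA graft" as early stopping rules, without saying whether the patient or the trial stops.

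Section 7c names Kaplan-Meier and Cox regression but states no analysis set, no censoring rule and no handling of patients taken off study. Section 4 (Outcomes) ends secondary patency at graft failure and does not define that term further. Section 2 makes secondary patency a primary outcome.

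**The concern.** An exclusion after randomisation that is triggered by the graft itself, and written for one arm, can remove that arm's failures from the comparison. A BCA graft taken out because the patient cannot tolerate it is lost as an access. If the patient is deleted or censored at that moment, the loss does not enter the secondary patency curve, whereas no written rule takes a comparable ePTFE patient off study. The error would run in the direction of Hypothesis 3A.

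The gap also leaves room for a late choice. The trial is unblinded (section 4c), and the section 7d footnote says "we will carry out a review of the outcomes every 6 months in this study". Unless the meaning of leaving the study is fixed in writing, it could be settled with outcomes in view.

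**Working it through.** **1. The passages side by side**

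| Section | Arm | Graft | Patient's place in the study | Analysis |
|---|---|---|---|---|
| 8a item 1 (intolerance) | BCA only | removed or replaced | off study | not stated |
| 8a item 3 (allergy) | BCA only | investigators decide | off study; unclear if only on removal | not stated |
| 4f | none named | investigators decide | not stated | not stated |
| 7d items 1-2 | BCA only | not stated | unclear whether patient or trial stops | not stated |
| 7c | both | - | - | no analysis set, no censoring rule |

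Three readings of leaving the study remain open: deleted, censored, or counted as a failure.

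**2. Inputs**

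- From section 7c: 50 patients per arm, two-sided alpha 0.05.
- From section 4b: two years of follow-up.
- Assumed, because the documents give no figure: share of BCA patients removed, q = 2% (1 of 50), 5% or 10%; true 2-year secondary patency S, equal in both arms, of 40.5%, 60.5% or 80%. The first two are the plan's BCA assisted-patency figures at 2 years and 1 year, used only as stand-ins. The 80% is added because, under the section 4 definitions, secondary patency should be at least as high as assisted patency.
- Also assumed: every off-study graft is a true failure, and time runs from placement.

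The plan has no figure of its own on this point. Its 49 per group for Aims 1-3 reproduces (60.5% v 30.5%, 80% power, continuity-corrected) and does not depend on it.

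**3. Overstatement of BCA patency if removed patients are deleted**

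Patent grafts are a share S of all patients, but the denominator shrinks to 1 - q, so the bias is S/(1 - q) - S.

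- q = 2%: 0.405/0.98 - 0.405 = 0.8 points; 0.605/0.98 - 0.605 = 1.2; 0.80/0.98 - 0.80 = 1.6.
- q = 5%: 0.405/0.95 - 0.405 = 2.1; 0.605/0.95 - 0.605 = 3.2; 0.80/0.95 - 0.80 = 4.2.
- q = 10%: 0.405/0.90 - 0.405 = 4.5; 0.605/0.90 - 0.605 = 6.7; 0.80/0.90 - 0.80 = 8.9.

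**4. Chance of a false BCA win**

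Log-rank simulation with exponential failure and removals spread over two years or over the first three months. The figure is the BCA side of the two-sided 0.05 test; it is 2.5% with no removals.

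| True patency, handling | 2% removed | 5% removed | 10% removed |
|---|---|---|---|
| 40.5%, deleted | 3.0% | 4.1-4.2% | 6.5-6.6% |
| 40.5%, censored | 3.1-3.5% | 4.3-5.7% | 7.0-11.3% |
| 60.5%, deleted | 3.3-3.4% | 5.0-5.1% | 10.0% |
| 60.5%, censored | 3.4-3.7% | 5.3-6.2% | 10.4-13.9% |
| 80%, either | about 4% | up to about 9% | 21-25% |

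**5. When the bias shrinks or vanishes**

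- Removal counted as failure on its date: 0 points at 2 years; false win 1.6-3.0% at patency of 40.5-60.5%. The departures from 2.5% reflect removal timing, since the curves agree at two years but not at every earlier time.
- Half of off-study patients lose the graft and the rest do as others do, deletion: the bias is S/(1 - q/2) - S. At q = 10% this is 0.405/0.95 - 0.405 = 2.1 to 0.605/0.95 - 0.605 = 3.2 points.
- Off-study patients have average patency, or the same rule and rate apply in both arms: no bias (2.4-2.6%).

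**The case against.** The strongest reply is that section 4f already covers this. Its heading speaks of treatment failure, it names no arm, and it covers removing or replacing a graft. Read with the definition of secondary patency, an explanted graft could be an event on its date in either arm, and the bias goes. Read as participant removal in both arms at equal rates, the bias also goes. But the text under that heading says neither thing, and section 8a states an off-study rule for one arm. Section 4f shows that an unbiased reading is available, not that it is the plan.

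Second, section 8a is a description of risks, and leaving the study may concern participation rather than data. That stands: nothing says that data are deleted. A reader might infer that the plan will drop BCA failures; the documents support only that it may.

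Third, outcomes are to follow a cited reporting standard that cannot be consulted here and might treat explantation as failure. So the absence of a rule is a statement about the protocol's own text.

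Fourth, removals are probably rare. Exclusion criterion 1 bars known allergy or intolerance, and section 8a says of BCA that "it is tested as non-antigenic and packaged sterile in its container". This bears on size, and it stands.

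**Conclusion.** The wording gap is certain: a one-arm off-study rule, no ePTFE counterpart, and no analysis set or censoring rule. The consequence is conditional. If removals occur and are deleted or censored, secondary patency is biased toward BCA; if they are counted as graft failure, it is not biased at 2 years.

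The size is undetermined. Over assumed patency of 40.5-80%, deletion overstates BCA by 0.8-1.6 points with 1 of 50 removed, 2.1-4.2 with 5% and 4.5-8.9 with 10%; across deletion and censoring, the false-win chance is about 3-4%, 4-9% and 6.5-25%. A reader might take the top figures as a worst case or a forecast. They are neither: the removal and patency rates are assumed, and higher values of either would give larger numbers.

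A reader might also extend the point to the other outcomes. Primary and assisted patency end at an intervention for stenosis or a first occlusion, so removal for intolerance is not itself one of their events. Re-intervention is not defined in the documents, and the direction of any effect there is not fixed. The point is limited to secondary patency. It should be fixed, because the outcome is primary and the remedy is cheap.

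**What to change.** Reconcile sections 4f, 7d and 8a on study participation, and leave the clinical decision about the graft as it is. Replace the off-study wording with:

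> Patients in either arm with graft intolerance, allergic reaction, or graft removal or replacement stay in follow-up through the three-monthly contacts to two years unless they withdraw consent. All randomised patients are analysed by assigned arm. Removal or replacement of the study graft for intolerance or allergy counts, in both arms, on its date as graft failure for secondary patency.

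Keep the section 4 definitions of primary and assisted patency for the main analysis, and add a sensitivity analysis that counts such removals as events.

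The cost is protocol and analysis-plan wording and a little more analysis; the three-monthly contacts are already planned. The BCA result may look slightly less favourable.
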